18. VALUATION OF SECURITY

18.1 Safety measurements

Figure (8.2.2) 1 - Research Program indicates safety measurements that are made in each visit or treatment period.

Security criteria

- Adverse events and visual ability

18.2 Times of Measurements

Clinical examination

Basal visit (Day 1)

The principal investigator or the head of the research team of the site duly specified must obtain the letter of informed consent of each of the subjects, before carrying out any procedure of the study.

When the informed consent is obtained and all the inclusion criteria and none of exclusion are met, a unique identification number of the subject will be assigned, this will be used throughout the study for its identification.

Female subjects who are of reproductive age will be tested for pregnancy in urine.

The following evaluations will be made:

Signature of informed consent

Review of inclusion criteria and exclusion criteria,

Demographics,

Urine pregnancy test (if applicable),

General and ophthalmological clinical history,

Clinical Photography,

Sampling of conjunctival sac fundus for culture,

Assigning number to the subject,

Delivery of medication,

Ocular symptoms: burning, tearing, foreign body sensation, pruritus, photophobia

Visual acuity and / or visual ability,

Anterior biomicroscopy: Conjunctival hyperemia, chemosis, secretion, palpebral edema, membranes and / or pseudomembranes, scales, epitheliopathy,

Fluorescein staining,

Green stain of lysine,
Posterior segment revision: Retina, Macula, Vitreous and Optic nerve.
Evaluation of adverse events.

This day the patient will be included, if clinically it suggests a bacterial conjunctivitis, it will be randomized and at that same moment a clinical photograph of his eyes will be made and a sample will be taken for culture of both eyes, immediately he will go with the person previously designated to randomize him, this person will not be masked and will give specific instructions to the patient on how to apply the study medication and will remember the importance of the patient not mentioning the study's evaluating physician how many times the treatment is applied, then he will start with the study medication regardless of the crop results.

Treatment visits:**Visit 1 (Day 3)**

Between the days of study there may be a window of \pm 1 day. If for any reason an assessment is made on any day not planned in the study, this information should be recorded in the unscheduled visit format found within the FRC.

At each follow-up visit, an ophthalmological examination will be performed in order to evaluate the following parameters.

1. Acuity and / or Visual Ability
2. Clinical Photography,
3. Evaluation of specific symptoms and signs: burning, tearing, foreign body sensation, pruritus, photophobia,
4. Anterior biomicroscopy: conjunctival hyperemia, chemosis, secretion, palpebral edema, membranes and / or pseudomembranes, scales, epitheliopathy.
5. Posterior biomicroscopy (retina, vitreous, macula and optic nerve).
6. Fluorescein staining
7. Green lysine stain
8. Evaluation of adverse events.
9. Evaluation of concomitant medications.

Final Visit (Day 8)

In this the following parameters will be evaluated:

1. Urine pregnancy test (if applicable)
2. Return of medication by the subject
3. Acuity and / or Visual capacity
4. Clinical photography,
5. Ocular symptoms: burning, tearing, foreign body sensation, pruritus, photophobia.
6. Conjunctival sac fundus sampling for culture
7. Anterior biomicroscopy: conjunctival hyperemia, chemosis, secretion, palpebral edema, membranes and / or pseudomembranes, scales, epitheliopathy.
8. Posterior biomicroscopy (retina, vitreous, macula and optic nerve).
9. Fluorescein staining
10. Green lysine stain.
11. Evaluation of adverse events
12. Evaluation of concomitant medications

Follow-up of Adverse Events (EA) (Day 23)

1. A telephone call will be made by the investigating doctor or responsible previously designated for the evaluation of adverse events.

19. PROOF OF PREGNANCY

The urine pregnancy test will be taken in the same facilities of the research center, where the subject will be given a bottle to collect their urine. This will be in private and then deliver the bottle with the urine sample to the investigating doctor or person in charge beforehand, who will introduce a test strip into the sample and wait for the result.

20. ADVERSE EVENTS

All adverse events should be subject to follow-up until their completion and documented in a complete and accurate manner in order to make possible the assessment of the safety of the study drug.

20.1 Events to be registered

An adverse event is defined as any unfavorable medical occurrence in a subject that is participating in a clinical trial, whether or not there is a causal relationship with the study drug and / or experimental procedures, that is present or detected as of the date that the patient signs the form of information and consent, regardless of the period of the study.

Therefore, the investigator will document as an adverse event:

- Any unfavorable and unintended sign, including an abnormal finding of an additional examination that the investigator considers clinically important,
- Any intercurrent symptoms or illness,
- Any worsening during the study of a symptom or disease already present when the patient entered the study (increase in frequency and / or intensity), and which:
 - It is detected during a study visit or in an additional examination,
 - Be present from the previous visit of the study and notify the patient.

A serious adverse event, that is, an event that, regardless of the dose of the study drug administered:

- How the patient's death results
- Be a threat to life,

Note: the term "threat to life" refers to an event in which the patient was at risk of death at the time of the event; it does not refer to an event that hypothetically could have caused death if it had been more serious.

- How persistent or important disability / disability results. Note: an event that seriously disrupts the patient's ability to lead a normal life, in other words that causes a significant change, deterioration, injury or alteration of the functions or body structure of the patient, physical activity and / or quality of life.
- Be a congenital anomaly / birth defect. Exposure to the study drug before conception (in man or woman) or during pregnancy that causes an adverse outcome in the child.

Note: any event that may not be an immediate threat to life or result in death or hospitalization but may endanger the patient or may require intervention to avoid one of these outcomes (eg, edema or allergic bronchospasm requiring treatment) intensive at home, blood dyscrasia, seizures that do not cause hospitalization, or development of drug dependence or drug abuse).

Consumption of the study drug by a person other than the patient:

- Minors: any consumption of the study drug with or without medical consequences must be notified immediately to the sponsor.
- Adults: any accidental consumption of the study drug with clinical symptoms and any intentional consumption of the study drug, with or without medical consequences, should be notified immediately to the sponsor.
- In these specific cases, the investigator must inform immediately by telephone or fax, or in non-working hours, to the 24-hour telephone line (see Table (12.3.1.3) 2). These cases should be reported on separate paper pages "Adverse Event" that will be provided to the centers and should be sent immediately by fax to the responsible person.
- A pregnancy that occurs during the study.

20.2 Methods for registration

Adverse events must be documented in an "Adverse Event" form. Some sections of the page must always be filled out in full, whether the event is serious or not serious. The other sections will be filled only when the event requires immediate notification.
In case of progression of the disease by episodes (chronic disease):

- If the disease was already known when the patient entered the study, it will only be documented as an adverse event when there is a worsening (increased frequency and / or intensity of episodes / attacks),
- If the disease is detected during the study and the repetition of the episodes allows diagnosing a chronic disease, episodes that clearly describe the diagnosis will be grouped in the same form "Adverse event".

20.3 Follow-up of adverse events

The researcher must ensure that the patient's follow-up is appropriate to the nature of the event, and that it continues until it is resolved. Any secondary deterioration should be reported immediately to the sponsor.

Any change in terms of diagnosis, intensity, severity, measures taken, causality or result related to an adverse event already reported should be written in a full evaluation of the event.

If the adverse event has not been solved in the patient's final visit, the study can not be closed until it has reached a resolution, which must be followed by the principal investigator or the previously assigned responsible person, who must look for it. detail of

the adverse event and its follow-up only if the researcher indicates that this adverse event is directly related to the study medication. If it is not directly related, then it must be registered and the center can be closed.

Report the initially not serious event on a paper page "Adverse event - Additional information" (see appendix 9),

- Report the deterioration caused by the seriousness on a paper page "Adverse event - Additional information" (see appendix 10), and
- Send them by email immediately to the responsible person indicated above.

If a female patient in the study becomes pregnant, the investigator should:

- Suspend the study treatment for the patient.
- Fill out an "adverse event" form of the FRC.
- Fill out a paper form of pregnancy follow-up report (first page, appendix 11),
- Contribute to the follow-up of this pregnancy and provide the sponsor with the information related to this follow-up (mainly using the second page of the pregnancy follow-up report).

21. EVALUATION OF CAUSALITY

It is important that the investigator of your opinion in relation to the cause-effect relationship between the adverse event and the study drug, for the following reasons: certain adverse events that occur during clinical investigations may be important enough to lead to changes in the drug development program (for example:

Changes in dose, population of the study or in the information provided to patients that may lead to the preparation of new forms of information and consent). This is especially true in case of events that are suspected to be related to the study drug (adverse reaction to the drug) and which, in its most severe form, mean a threat to life.

The causality must be assessed at the time of writing in the patient's file; Subsequently, the reports of a serious and non-serious adverse event will be filled out in its various formats. Only cases marked by the researcher as "related" or according to the opinion of the sponsor have a causal relationship with the investigational medicinal product under reasonable suspicion (relationship of the Adverse Event with the mechanism of action of the drug under study, ...) they will be considered as an Adverse Reaction to the suspect medication.

In general, the expression reasonable causal relationship means communicating that there is evidence or arguments to suggest a causal relationship.

22. RESPONSIBILITIES OF THE SPONSOR

Independently of the normative obligations of the researcher, the sponsor must report the pharmacovigilance data to the pertinent Authorities and to all participating researchers, in accordance with the requirements established in the International Conference on Harmonization (ICH), in the guidelines of the Good clinical practices and local regulations.

23. STATISTICS

Sample size

We conducted a review of published articles regarding the use of medications in the treatment of bacterial conjunctivitis. We found three publications that are the following:

- 1) "Gatifloxacin Ophthalmic Solution for Treatment of bacterial Conjunctivitis: Safety, Efficacy and Patient Perspective". Clyde Schultz. En Ophthalmology and Eye Diseases. 2012:4 65-70.
- 2) "Microbiological Efficacy of a New Ophthalmic Formulation of Moxifloxacin Dosed Twice-Daily for Bacterial Conjunctivitis". Shachar Tauber et.al. En Adv Ther. (2010) 28(7):566-574.
- 3) "Clinical use of gatifloxacin ophthalmic solution for treatment of bacterial conjunctivitis". Lorenzo J. Cervantes y Francis S. Mah. En Clinical Ophthalmology. 2011:5 495.502.

The first of the publications referred to here (Clyde Schultz) is a review article that summarizes the findings regarding the use of gatifloxacin mainly as a treatment for bacterial conjunctivitis but does not give precise figures, it only says, for example, that the Effectiveness reported in an article made in China was around 93%. It is not an original article that gives specific results, but rather comments findings and issues an opinion regarding the convenience of using them as an effective and safe treatment for bacterial conjunctivitis.

The second revised article (Schachar Tauber) is an original article. This is a multicentre study in which 1180 patients were recruited throughout the United States of America, who had a clinical diagnosis of bacterial conjunctivitis. All patients were given a sample

prior to treatment and another at the end of treatment, which were sent to the clinical laboratory where standard methods of microbiology were used to isolate the biological specimens before and after the treatments. One group was treated with MOXI-AF and the other with placebo (vehicle) instilling in the conjunctival sac one drop twice a day for three days and the most important results of this investigation are summarized in Table 1.

The third article reviewed (Cervantes) describes other studies conducted to test gatifloxacin in two presentations: Zymar (0.3%) tested in 52 patients treated for three days vs. placebo (vehicle) tested in 48 patients and Zymaxid (0.5%) tested in 333 patients for three days vs. placebo (vehicle) tested in 325 patients for three days.

The results reported in these articles regarding efficacy can be summarized in Table 1.

Cuadro 1. Eficacia de medicamentos para erradicación de bacterias en infecciones oculares (Conjuntivitis) reportada en publicaciones.

Tratamiento	Eficacia Absoluta	Total ojos		Eficacia %
		n	n	
MOXI-AF¹		424	316	74.53%
Placebo (Vehículo)¹		423	237	56.03%
Zymar²		52	40	76.92%
Placebo (Vehículo)²		48	28	58.33%
Zymaxid²		333	193	57.96%
Placebo (Vehículo)²		325	148	45.54%

Tratamiento	Eficacia específica por bacteria			
MOXI-AF¹	Haemophilus influenzae	67	66	98.51%
	Streptococcus pneumoniae	22	19	86.36%
	Staphylococcus aureous	17	16	94.12%
Placebo (Vehículo)¹	Haemophilus influenzae	52	31	59.62%
	Streptococcus pneumoniae	18	9	50.00%
	Staphylococcus aureous	15	12	80.00%
Zymar²	*	52	48	92.31%
Placebo (Vehículo)²	*	48	34	70.83%
Zymaxid²	*	333	301	90.39%
Placebo (Vehículo)²	*	325	228	70.15%

* **Nota:** La eficacia específica por bacteria en los estudios con Zymar y con Zymaxid no se presenta para cada bacteria sino para la totalidad de bacterias que aparecieron en el cultivo inicial y ya no aparecieron en el cultivo post-tratamiento.

¹ Microbiological Efficacy of a New Ophthalmic Formulation of Moxifloxacin Dosed Twice-Daily for Bacterial Conjunctivitis. Shachar Tauber et.al. En Adv Ther. (2010) 28(7):566-574.

² Clinical use of gatifloxacin ophthalmic solution for treatment of bacterial conjunctivitis.

Lorenzo J. Cervantes y Francis S. Mah. En Clinical Ophthalmology. 2011:5 495-502.

To calculate the sample size, we obtained the overall average of absolute efficacy for patients treated with some medication and for patients treated with placebo. For patients treated with medication, the absolute efficacy (total disappearance of bacteria in the post-treatment culture) was 69.8% and for those treated with placebo it was 53.3%. The specific efficacy (disappearance of a specific bacterium that was present in the pre-treatment culture) for the groups treated with some medication was 92.34% and for patients treated with placebo 66.12%.

With these figures, we can calculate the sample size needed to detect that level of differences reported between patients with bacterial conjunctivitis treated with medication vs. patients treated with placebo.

Annex 1 develops the calculations for the sample size necessary to detect the differences in the percentage of efficacy to eliminate bacteria from patients with bacterial

conjunctivitis found in the articles reviewed between patients treated with any drug vs patients treated with placebo. The Fleiss formula is used for case-control studies.

From the calculations made we can draw the following conclusions and recommendations. The average absolute efficacy found in the articles commented is almost 70% (69.8%) for patients treated with any medication and only 53.3% for patients treated with placebo (in this case vehicle was used as a placebo). According to the Fleiss formula for cases and controls, a sample of 147 cases per group assures us that if the differences that we are going to prove between the treatments is of that magnitude (69.8 %% vs 53.3%) or greater, we will have a 80% probability that the statistical test that we apply to evaluate the differences will be statistically significant (Power or power of the sample), and on the other hand, if the differences between the treatments were not of that magnitude (the differences were of lesser magnitude), when applying a statistical test on the results of a sample of 147 cases with minor differences to the ones presented, it will be not significant and the probability of this happening will be 0.95 (Reliability of the sample).

In summary, to prove differences in the absolute efficacy of two treatments in which one has almost 70% absolute efficacy and the other of only 53.3%, a sample of 147 cases per group will be necessary to have a reliability of 95% and a 80% power.

If instead of calculating the sample size with absolute efficiency we calculate it with the specific efficacy for specific bacteria, using the percentages that we obtained from the review of the articles published and that were 92.34% and 66.12% for patients treated with some medication and for those treated with placebo respectively, the sample according to the Fleiss formula for a 95% reliability and a power of 80% is 44 patients per group.

We can suggest that the minimum sample should be 50 eyes per treatment group and if possible, it would be desirable that the sample per group could reach 150 cases per group.

Of course, the theoretical calculations are a part of the sample size problem, the other part refers to the resources available. Given that 5 medications are going to be tested: Vigamoxi®, Zymar®, and PRO-157 in three posologies and probably a placebo group as long as this does not contravene ethical aspects, if the sample were 50 eyes per group, it would imply 250 or 300 cultures and studies of microbiology or PCR before the treatments and another at the end of them. If the sample increased to 150 eyes per group, then these figures would triple. In short, the theory indicates that an adequate sample to establish and confirm statistically differences in the magnitudes reported in other studies between drug treatments and placebo treatments should be approximately between 50 and 150 eyes.

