Ha: The ophthalmic solution PRO-157 is so safe and effective in some of its different posologies when demonstrating non-inferiority when compared against Moxifloxacin and Gatifloxacin in the treatment of conjunctivitis	

Sponsor's name: Laboratorios Sophia, S.A. of C.V.

Finished Product Name: NA

Active Ingredient Name: Pazufloxacin

Methodology

Multicentric double randomized study masked.

Number of participants: 300 eyes, 60 eyes per treatment group

Diagnosis and main criteria for inclusion

Patients with bacterial conjunctivitis (signs and / or symptoms and / or culture)

Subjects aged 0 years to 99 years.

Study medication:

Pazufloxacin

- **Treatment duration:**
- - **Recruitment period: 4 months**
- - **Period of treatment: 7 days**
- - **Period of follow-up: 15 days**

Criteria for evaluation:

Efficacy measurements:

Main efficacy criterion

It will be determined as effective if there is a reduction in the number or species of bacterial flora comparing the basal culture against the final between the five different groups of patients and / or if there is a reduction or absence of the infection with the clinical evaluation through signs and symptoms such as: burning, tearing, foreign body sensation, pruritus,

photophobia, conjunctival hyperemia, chemosis, secretion, palpebral edema, membranes and / or pseudomembranes, palpebral scales and epitheliopathy

Security measurements:

Visual ability

Adverse events

INDICE

1. Summary of the study	2
2. Glossary and definitions	6
3. Administrative structure of the study	7
3.1 Parties not sponsored.	7
3.2 Sponsored parties	8
4. Background information	8
4.1 Justification	9
4.2 Non-clinical pharmacology	11
5. Clinical Studies	17
6. Hypothesis and Objectives	17
6.1 Work hypothesis	17
6.2 Objectives.	19
7. Point or points limit	19
8. Study plan	25
9. Measures to minimize deviations	29
10. Products administered	30
11. Description of the packaging	31
12. Management of the study medication	31
13. Closure of the center	33
13.1 Premature discontinuation of study	31
13.2 Center closure	31
14. Source data	33
15. Selection and withdrawal of subject of study	33
15.1 Inclusion criteria	33
15.2 Exclusion criteria	34
15.3 Criteria for patient withdrawal	36
16. Treatment of the study subjects	37
16.1 Managed treatments	37
16.2 Delivery of treatment	37
16.3 Previous and concomitant treatments	37
16.4 Treatments authorized during the study	39
16.5 Drug compliance	39
17. Methods and times of measurements	39

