6 HYPOTHESES AND OBJECTIVES OF THE STUDY

6.1 Working hypothesis

The ophthalmic solution PRO-157 is so safe and effective in any of its different posologies when demonstrating non-inferiority when compared against Moxifloxacin and Gatifloxacin in the treatment of bacterial conjunctivitis.

Ho: The ophthalmic solution PRO-157 is not as safe and effective in any of its different dosages when it shows no inferiority when compared to Moxifloxacin and Gatifloxacin in the treatment of conjunctivitis.

Ha: The ophthalmic solution PRO-157 is so safe and effective in some of its different posologies when demonstrating non-inferiority when compared against Moxifloxacin and Gatifloxacin in the treatment of conjunctivitis.

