7 STUDY DESIGN

7.1 Point or limit points

Criteria for the evaluation.

Efficacy measurements:

Main efficacy criterion

Efficacy will be determined by taking cultures of the lower conjunctival cul-de-sac background quantifying (colony-forming units) and identifying genus and basal and final microbial species.

It will be determined as effective if there is a reduction in the number or species of bacterial flora comparing the basal culture against the end between the five different groups of patients and / or if there is a reduction or absence of the following specific signs and symptoms: burning, tearing, Foreign body sensation, pruritus, photophobia, conjunctival hyperemia, chemosis, palpebral edema and secretion, membranes and / or pseudomembranes when comparing the study medication versus Moxifloxacin and versus Gatifloxacin from baseline to final visit.

Efficiency parameters

- The effectiveness of the drug will be evaluated by means of:

1. Clinical referral

2. Microbiological remission

Clinical remission will be evaluated by means of the signs and symptoms that the patient presents at the beginning and at the end of the study.

Variable	Operationalization	Measurement scale	Value
Secretion	Dependent Qualitative ordinal	Absent Present	Must be recorded as absent in 95% of the subjects evaluated
Conjunctival hyperemia	Dependent Qualitative ordinal	Absent Mild Moderate Severe	You must comply with the following: • Absent \geq 95.0% • Mild \leq 5.0% • Moderate \leq 2.5% Severe \leq 1.0%
Chemosis	Dependent Qualitative ordinal	Absent Present	Must be recorded as absent in 95% of the subjects evaluated
Eyelid edema	Dependent Qualitative ordinal	Absent Present	Must be recorded as absent in 95% of the subjects evaluated
Corneal epithelial defects	Dependent Qualitative ordinal	Affected area, percentage	Percentage of affected area less than 95%

The microbiological remission will be evaluated by means of the culture taken from the conjunctival sac fundus.

Variable	Operationalization	Measurement scale	Value
Culture	Dependent Discrete quantitative	UFC * / ml Eradication Reduction Proliferation	Must be recorded as absent in 95% of the subjects evaluated

* Colony forming units

The drugs under study will be considered effective if the patient has any of the following:

1. Clinical remission + Microbiological remission.
2. Clinical referral.
3. Microbiological remission.

Security measurements:

Adverse events and visual capacity.

Evaluation parameters

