8 STUDY PLAN

This is a phase II, randomized, double masked, multicentre, national study.

This study will be carried out with 60 eyes with diagnosis of bacterial conjunctivitis, by treatment group, of patients of the ophthalmological consultation.

Patients diagnosed with bacterial conjunctivitis (signs and / or symptoms and / or culture) recruited will be treated for 7 days with any of the three posologies of PRO157, Moxifloxacin, or Gatifloxacin. The randomization of any of the medications will be coordinated by a member of the research team previously designated who will not be masked and will be responsible for indicating to the patients how to apply the drops, emphasizing the patients of by no means mentioning the evaluating physician with the frequency who applies the study medication.

No patient may use the aforementioned treatment more than the prescribed time. For purposes of the protocol, the infected eye (s) will be taken into account at baseline but the study medication and procedures will be applied and will always be done in both eyes to protect the healthy eye and the possibility of infection if Do not be infected from the beginning.

The study is divided into the following periods:

There will be a total of 3 visits which are divided into 1 baseline visit (day 1) 1 treatment visits (day 3), 1 final visit (day 8). A telephone call will finally be made to evaluate adverse events after 15 days of the last application of medication (day 23)

At each visit from the baseline a clinical photograph of the eyes will be made, each of them must be identified by patient and visit number and delivered once the 30 patients are completed on a CD or USB.

1. Period of treatment of 7 days (from day 1 to 7) where any of the following posologies are applied according to randomization:

PRO157 1 drop 2 times a day in both eyes.
PRO157 1 drop 3 times a day in both eyes.
PRO157 1 drop 4 times a day in both eyes.
Moxifloxacin 1 drop 3 times a day in both eyes
Gatifloxacin1 drop 3 times a day in both eyes

The study medications will be delivered by a coordinator (not blinded) or a person previously designated by the principal investigator, who will indicate how to apply the study medication according to the randomization and will place special emphasis on not mentioning the principal investigator or designee. perform the evaluations as the drop or any characteristic of the jars is applied.

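### Non-inferiority to two active drugs is hypothesised without a margin, while the sample size is calculated for a drug-versus-placebo contrast the trial never makes

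*Combined protocol and SAP*

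**What the plan says.** Section 6.1, repeated in the Summary, gives the alternative hypothesis as "PRO-157 is so safe and effective in some of its different posologies when demonstrating non-inferiority when compared against Moxifloxacin and Gatifloxacin". The supplied text contains no numeric margin, non-inferiority test or confidence-interval rule. Under the analysed data sets in Section 23, the intention-to-treat population is used for description, and the only inferential step named is a bivariate analysis in the per-protocol population.

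Section 23 sizes the study by computing the "sample size needed to detect that level of differences reported between patients with bacterial conjunctivitis treated with medication vs. patients treated with placebo". For absolute efficacy (69.8% on drug, 53.3% on placebo) it concludes that "a sample of 147 cases per group will be necessary to have a reliability of 95% and a 80% power". For specific efficacy (92.34% and 66.12%), "the sample according to the Fleiss formula for a 95% reliability and a power of 80% is 44 patients per group". It then suggests at least 50 eyes per group and ideally 150, notes that resources also matter, and mentions "probably a placebo group as long as this does not contravene ethical aspects".

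The design itself has no placebo. In Section 8 patients "will be treated for 7 days with any of the three posologies of PRO157, Moxifloxacin, or Gatifloxacin", and Section 16.1 lists the same five arms. The Summary fixes the size as "Number of participants: 300 eyes, 60 eyes per treatment group".

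Section 7.1 states: "The drugs under study will be considered effective if the patient has any of the following". The list that follows is clinical remission, microbiological remission, or both. The sizing uses bacterial eradication on culture alone.

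**The concern.** The sizing answers a different question from the hypothesis. A calculation for detecting a drug-placebo difference says nothing about the chance of excluding a given loss of efficacy against an active comparator. That chance depends on a margin, and none is set. As written, no pre-set rule lets the data accept or reject the alternative hypothesis. The likely substitutes, a margin chosen after the results are known or a non-significant difference read as non-inferiority, would not be credible. The stated 80% power would meanwhile be taken to apply to this trial when it does not. The hypothesis can also be met by one of three posologies tested against two comparators, and no rule says how those six comparisons combine.

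**Working it through.** **1. The plan's own figures.** Annex 1 uses the Fleiss formula with two-sided α = 0.05 (z = 1.960), 80% power (z = 0.842) and 1:1 allocation.

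- Absolute efficacy, 0.698 vs 0.533: m′ = 135.27; with continuity correction 147.1 (plan: 147).
- Specific efficacy, 0.9234 vs 0.6612: m′ = 36.37; corrected 43.7 (plan: 44).

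The arithmetic is right. The four rates are unweighted means of the rows of Cuadro 1. For the contrast the plan did size, 60 per group would give 46% power on absolute and 95% on specific efficacy (38% and 92% with continuity correction), but the trial contains no such contrast.

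**2. Smallest margin that 60 per arm supports.** Assumptions: independent, evaluable eyes; equal true rates p; one-sided α = 0.025. SE = √(2p(1−p)/60), and the margin for 80% power is (1.960 + 0.842) × SE.

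- p = 0.698: SE = 0.0838; margin = 23.5 points. The cited drug-placebo difference is 69.8 − 53.3 = 16.5. Inverse-variance pooling of the three absolute rows of Cuadro 1 gives 16.2 (95% CI 11.5 to 20.9).
- p = 0.9234: SE = 0.0486; margin = 13.6 points. The cited difference is 92.34 − 66.12 = 26.2.

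**3. Power at assumed margins M.** Against one comparator, power = Φ(M/SE − 1.96). Against both, the two test statistics have correlation 0.5 because they share the PRO-157 arm. The margins 8.25 and 13.1 are half the plan's drug-placebo differences, an illustrative choice.

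| Rate | Margin (points) | One comparator | Both comparators |
|---|---|---|---|
| 69.8% | 8.25 | 16% | 7% |
| 69.8% | 16.5 | 50% | 34% |
| 92.34% | 10 | 54% | 37% |
| 92.34% | 13.1 | 77% | 65% |
| 92.34% | 15 | 87% | 79% |

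At 92.34% and the full 26.2 points, power against one comparator exceeds 99.9%.

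**4. Three posologies.** These figures come from simulation with 2,000,000 normal draws and shared comparator arms. The chance that at least one of three equally effective posologies succeeds against both comparators is:

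- 69.8%, margin 16.5: 60% unadjusted; 39% with Bonferroni over three.
- 92.34%, margin 13.1: 88% unadjusted; 74% with Bonferroni.

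If all three posologies lie exactly at the margin against one comparator and the other comparator is not limiting, the false-positive rate for at least one success is about 6.3% unadjusted and 2.2% with Bonferroni, against a nominal 2.5%.

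**The case against.** The strongest reply is that this is a Phase II study whose size openly reflects resources, that 60 lies inside the 50-to-150 range in Section 23, and that Sections 7.1 and 8 describe a different setting from the cited studies: an either/or endpoint and 7 days of treatment rather than 3. An either/or success rate cannot be lower than the eradication rate alone. At an assumed 85%, the smallest margin with 80% power falls to 18.3 points, and at 90% to 15.3. So underpowering on absolute efficacy is conditional on the plan's own 69.8%. That condition stands, and it is why 60 cannot simply be called too few. The reply does not supply a margin, and the 50-to-150 range was itself derived for drug against placebo.

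Three further points:

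- Section 7.1 does set numeric targets, such as a sign being absent in 95% of subjects. These are within-group thresholds, not a between-arm rule, but they must be reconciled with any new criterion.
- The 26.2-point specific difference is an unweighted mean. Inverse-variance pooling of the five specific rows gives 23.0 (95% CI 18.1 to 27.9). Half of that is 11.5, where power against one comparator is about 66%. This makes the specific case less favourable.
- The 6.3% applies if one successful posology is enough, as the alternative hypothesis says. The working hypothesis refers to any posology; if every posology had to succeed, there would be no inflation, but power would fall.

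**Conclusion.** The concern holds. The hypothesis is non-inferiority to two active drugs, no margin is stated, both power calculations concern a placebo contrast absent from the design, and 60 per group is not derived. On the plan's absolute efficacy rate, 60 eyes per arm reaches 80% power only with a margin of 23.5 points. A product meeting that margin could be no better than vehicle on the plan's own 16.5-point difference. On the specific rate the required margin is 13.6 points, and adequacy depends on the margin chosen.

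These figures assume equal true rates, one-sided 2.5%, and 60 independent evaluable eyes per arm. That is favourable: Section 8 allows both eyes of a patient to count, and Section 15.1 lets culture-negative patients continue. The mismatch itself does not depend on these assumptions and must be fixed before the trial can support its stated claim.

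**What to change.** Amend the Summary and Sections 6.1, 7.1 and 23 as follows.

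1. Name one efficacy endpoint for the non-inferiority test. Reconcile culture eradication with the either/or definition and the 95% targets in Section 7.1. Say whether the claim covers efficacy only, since the hypothesis also mentions safety.
2. State a numeric margin justified against the drug-placebo difference for that endpoint. Allow for the uncertainty of that difference, and for the fact that the source data come from 3-day regimens while this trial treats for 7 days.
3. Test with a one-sided 97.5% confidence bound, and name the analysis population.
4. State whether success requires both comparators, and how the three posologies are handled, for example by Bonferroni or a fixed testing order.
5. Replace the placebo-based 80% statement with the power of 60 eyes per arm at that margin.

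If that power is too low, restate the aim as estimating between-arm differences with 95% confidence intervals and withdraw the non-inferiority claim. The half-width is 1.96 × SE: about 16 points at 69.8% and 9.5 at 92.34%.

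The cost is wording, handled as an amendment under Section 29.2, with no extra patients. The stated power becomes less favourable, and a multiplicity rule lowers it further. Insisting on 80% power at a narrow margin would require more eyes.
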